#### 14.3 Analysis Populations

In this study, 3 types of analysis population will be used.

Identification Number:
FORM-000050125
Previous Doc Number:
CTWI10A

Version Number: 1.0, CURRENT

#### **Protocol Template**

Sponsor: Menarini Pharmaceutical Study Code: MEIN/19/ZoNe-HYP/001

Protocol Version\_1 of 16/07/2020

- Enrolled population: Patients who are enrolled into the study and may or may not receive the study drug (extemporaneous combination)
- Intent-to-Treat population: Patients who are in the Enrolled population and receive at least 1 dose of study drug (combination therapy) and have at least 1 post baseline safety assessment
- Safety population: Patients who are in the Enrolled population and receive at least
   1 dose of study drug (combination therapy)
- Per protocol population: All patients included in the safety population who do not have any major protocol deviations will be included in this population

## 14.4 Analysis Variables

Analysis of Variables and Populations Used				
Efficacy				
	Analysis Variables	Population Used		
Primary efficacy	Change in mean sitting DBP between Week 0 (Visit 2) and Week 8	ITT population,		
1 Illiary Cilicacy	(Visit 3)	PP population		
Secondary efficacy	Change in mean sitting SBP between Week 0 (Visit 2) and Week 8	ITT population,		
Secondary efficacy	(Visit 3)	PP Population		
	Number and proportion of patients achieving the BP goal (sitting BP ITT pop			
	≤130/80 mmHg) at Week 0 (Visit 2) and Week 8 (Visit 3)			
	Adherence to treatment will be measured through treatment	Enrolled population,		
	compliance which is 100 × (actual doses taken/ planned doses)  Safety popul			
Exploratory efficacy	Change in mean sitting SBP and DBP between Visit 1 and Visit			
	2 in the group of patients on ZOF 30 and NEB 5 mg and in the			
	group of patients switched to ZOF 30 mg or NEB 5 mg from			
	any other ACE-I and BB			
	Change in mean sitting SBP and DBP between Visit 1 and Visit	Enrolled Population		
	3 in the group of patients on ZOF 30 mg and NEB 5 mg or in			
	the group of patients switched to ZOF 30 mg or NEB 5 mg from			
	any other ACE-i and BB			
	Number and proportion of patients in the group of patients on			

Identification Number: FORM-000050125

Previous Doc Number: CTWI10A

Version Number: 1.0, CURRENT

#### **Protocol Template**

Sponsor: Menarini Pharmaceutical Protocol Version\_1 of 16/07/2020
Study Code: MEIN/19/ZoNe-HYP/001

	ZOF 30 and NEB 5 mg and in the group of patients switched to	
	ZOF 30 mg or NEB 5 mg from any other ACE-I and BB	
	achieving the BP goal (sitting BP ≤130/80 mmHg) at Visit 2 and	
	Visit 3 suggested in Section 6	
Safety	Safety and tolerability of the extemporaneous combination between	Safety population
	NEB 5 mg and ZOF 30 mg measured by AEs, SAEs, AEOSI, vital	
	signs, physical examination, ECG, and concomitant medications at	
	Week 0 (Visit 2) and Week 8 (Visit 3)	
	OCL -1 DDD dietal	

AE: adverse event; AEOSI: adverse event of special interest; BP: blood pressure; DBP: diastolic blood pressure; ECG: electrocardiogram; ITT: Intent-to-treat; SAE: serious adverse event; NEB: nebivolol; SBP: systolic blood pressure; ZOF: zofenopril calcium

#### 14.5 STATISTICAL ANALYSIS

#### 14.5.1 Descriptive Statistics

Patient disposition, demographics and baseline characteristics, medical history, and prior and concomitant medication will be summarized by treatment group as well as overall.

Continuous variables will be summarized with the number of non-missing observations, mean, SD, standard error of the mean, minimum, median, and maximum. Categorical variables will be presented with the number of non-missing observations and column percentages (n, %).

#### 14.5.2 Primary (efficacy) Analysis

The primary efficacy analysis will be conducted on the intent-to-treat (ITT) population. The interpretation of results will be based on ITT population. The PP population will be used to assess the robustness of the results obtained using the ITT population.

The primary endpoint is the mean change from baseline in sitting DBP at Week 8 (Visit 3) for patients who are receiving combination therapy.

The statistical hypothesis will be defined as below:

H0: There is no change in the sitting DBP prior or post combination therapy

H₁: There is a difference in the sitting DBP prior or post combination therapy

Identification Number: FORM-000050125

Previous Doc Number:
CTWI10A

Version Number: 1.0, CURRENT

#### **Protocol Template**

Sponsor: Menarini Pharmaceutical Study Code: MEIN/19/ZoNe-HYP/001

Protocol Version\_1 of 16/07/2020

The above hypothesis will be tested as following-

- Change from baseline in sitting DBP from prior and post combination therapy will be compared using paired t-test. The p-value will be presented using paired t-test.
- The primary endpoint will be presented in a descriptive manner using n, mean, median, SD, Q1, Q3, and minimum and maximum.
- Assumption of normality will be investigated using Wilk-Shapiro test. If violation is observed, then paired t-test will be replaced by Wilcoxon signed rank test.

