#### 14.2 Determination of Sample Size

Considering a screen failure and a drop-out rate of 25% from Visit 1 and Visit 3, the number of patients to be screened is 290. Two-hundred and sixteen with uncontrolled hypertension, are planned to be included at Screening in the assessment period lasting for 8 weeks. A total sample size of 216 patients is required to achieve 90% power at 5% significance level assuming a difference in mean DBP from baseline to 8 weeks of 4 mmHg and a standard deviation (SD) for this difference of 10 mmHg. The mean change in DBP for null hypothesis is set at 2 mmHg.

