### 2.4. ESTIMANDS

Estimand	Definition	Attributes			
		Population	Variable/Endpoint	Intercurrent event handling strategy	Population- level summary measure
Primary Estimand		Intent-To- Treat (ITT)	Change in mean sitting DBP between Week 0 (Visit 2) and Week 8	The patients will not be permitted to use any of the Blood pressure modifying medications from Screening till the end of treatment.	Difference in mean DBP with P-value
Secondary Estimand 1		Intent-To- Treat (ITT)	Change in mean sitting SBP between Week 0 (Visit 2) and Week 8	The patients will not be permitted to use any of the Blood pressure modifying medications from Screening till the end of treatment.	Difference in mean SBP with P- value
Secondary Estimand 2		Intent-To- Treat (ITT)	The number of patients achieving BP goal (sitting BP ≤130/80 mmHg)	The patients will not be permitted to use any of the Blood pressure modifying medications from Screening till the end of treatment.	Difference in proportion of patients achieving BP goal between Week 0 (Visit 2) and Week 8 with P-value

Document: \\ieedc-vnasc01\BIOSdata\Menarini\NebZof\KZA41200\Biostatistics\Documentation\SAP

Author: [name] Version Number: Final V1.0

Version Date: [14Dec2021]

Template No.: CS\_TP\_BS016 Revision 6 Reference: CS\_WI\_BS005

Page 13 of 37

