#### 16.1.3. PRIMARY ANALYSIS OF PRIMARY EFFICACY VARIABLE

The primary objective of this study is to test the hypothesis that

- H0: There is no change in the sitting DBP prior or post combination therapy
- H1: There is a difference in the sitting DBP prior or post combination therapy.

The primary efficacy analysis will be performed for the ITT population. The above hypothesis will be tested as following-

• Change from baseline in sitting DBP from prior and post combination therapy will be compared using paired t-test. The p-value will be presented using paired t-test.

Document: \\ieedc-vnasc01\BIOSdata\Menarini\NebZof\KZA41200\Biostatistics\Documentation\SAP

Author: [name] Version Number: Final V1.0

Version Date: [14Dec2021]

Template No.: CS\_TP\_BS016 Revision 6 Reference: CS\_WI\_BS005

Page 26 of 37

- The primary endpoint will be presented in a descriptive manner using n, mean, median, SD, Q1, Q3, minimum and maximum.
- Assumption of normality will be investigated using Wilk-Shapiro test. If violation is observed, then paired ttest will be replaced by Wilcoxon signed rank test.

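### The normality pre-test can swap the primary paired t-test for a Wilcoxon test, so the p-value may no longer concern the mean DBP change that the endpoint, estimand and sample size name

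*Protocol*

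**What the plan says.** Protocol 14.5.2 defines the primary endpoint as a mean change in sitting DBP at Week 8. The planned test is: "Change from baseline in sitting DBP from prior and post combination therapy will be compared using paired t-test". It then adds a data-dependent step: "If violation is observed, then paired t-test will be replaced by Wilcoxon signed rank test".

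SAP 16.1.3 repeats this: "Assumption of normality will be investigated using Wilk-Shapiro test", then "If violation is observed, then paired ttest will be replaced by Wilcoxon signed rank test". SAP 3.3, which lists changes from the protocol, leaves the rule alone. Neither section gives a level for the normality test; SAP 6.5 sets a two-sided 5% default. Both sections list n, mean, median, SD, quartiles and range for the endpoint. Neither plans the t-test alongside the Wilcoxon test, or an estimator that belongs to the Wilcoxon test.

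The population-level summary in SAP 2.4 is: "Difference in mean DBP with P-value". Protocol 14.2 also sizes the trial on a mean: "A total sample size of 216 patients is required to achieve 90% power at 5% significance level", with a mean change of 4 mmHg, an SD of 10 mmHg and a null mean of 2 mmHg. The hypothesis itself is looser: "H0: There is no change in the sitting DBP prior or post combination therapy".

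The same switch applies to SBP (Protocol 14.5.4, SAP 16.2.2) and to the exploratory Visit 1 to Visit 3 changes (Protocol 14.5.5, SAP 16.3.2).

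**The concern.** The primary test is not settled until the data are seen, and the two candidates answer different questions. The t-test addresses the mean change. The signed-rank test addresses the pseudo-median (the median of averages of two patients' changes), which equals the mean only when changes are symmetric. After a switch, the report would set a mean beside a p-value that does not test it.

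The pre-test also has little to protect. With about 216 changes the sample mean is close to normal for moderately non-normal data, while Shapiro-Wilk at that size detects departures that do the t-test no harm. The pre-test therefore tends to move the analysis away from a valid test of the mean. Under skewness it moves it to a test that rejects a true zero mean more often than 5%.

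**Working it through.** **Inputs.** Protocol 14.2: n = 216, SD 10 mmHg, planned mean 4 mmHg, sizing null 2 mmHg, power 90%, level 5%. SAP 6.5: two-sided tests at 5%. Assumed: Shapiro-Wilk at 5%; skewness from 0.3 to 1.0, using shifted gamma distributions.

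**1. The plan's own figure.** For a single mean, n = (SD × (z_alpha + z_power) / delta)², with delta = 4 − 2 = 2. One-sided: (10 × (1.645 + 1.282) / 2)² ≈ 214, which becomes 216 with the exact t calculation. So 216 is reproduced, and it is a sample size for a mean. (It needs a one-sided 5% test; the two-sided version gives 265. That is a separate matter.)

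**2. Error rate when the true mean change is zero.** 10,000 simulated trials per row, n = 216, SD 10. The Monte Carlo standard error near 5% is √(0.05 × 0.95 / 10,000) = 0.2 percentage points.

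| Distribution of changes | Switch to Wilcoxon | t-test always | Two-stage rule |
|---|---|---|---|
| Normal | 5% | 5.3% | 5.4% |
| t, 5 df (symmetric) | 85% | 5.0% | 5.1% |
| Uniform (symmetric) | 100% | 5.0% | 5.0% |
| Skewness 0.3 | 34% | 5.2% | 6.2% |
| Skewness 0.5 | 76% | 4.8% | 9.0% |
| Skewness 0.75 | 98% | 4.9% | 14.4% |
| Skewness 1.0 | 100% | 5.2% | 22.4% |

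Further independent runs gave two-stage rates of 5.5-6.6%, 8.3-9.5%, 14.2-14.9% and 21.2-22.0% for the four skewed rows. With 180 evaluable patients the two-stage rate is 8.3% at skewness 0.5 and 20.3% at 1.0; the t-test gives 5.1% and 4.9%.

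**3. Hand check of the mechanism.** With mean zero and SD 10, the simulated pseudo-median lies 0.25, 0.41, 0.61 and 0.84 mmHg from the mean at skewness 0.3, 0.5, 0.75 and 1.0. The standard error of the mean is 10 / √216 = 0.680 mmHg. Taking this as roughly the precision of the pseudo-median too, the Wilcoxon statistic is off-centre by d = 0.41 / 0.680 = 0.60 at skewness 0.5. Its two-sided rejection rate is then about Φ(−1.96 + 0.60) + Φ(−1.96 − 0.60) = 0.087 + 0.005 = 9.2%, against 9.1% simulated for Wilcoxon alone. At skewness 1.0, d = 0.84 / 0.680 = 1.235, giving about 23.5% against 22.4% simulated.

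**4. At the planned effect.** With a true mean change of 4 mmHg tested against zero, the mean is 4 / 0.680 = 5.9 standard errors from the null. In simulation over skewness −1.5 to 1.5 the t-test rejected in 100% of trials and the two-stage rule in at least 99.5%. They disagreed in no trial at skewness ±0.5 and in at most 0.5% overall.

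**5. Nearer the null.** For true changes of about 1-2 mmHg with skewness 0.5, the two rules disagreed in 8-18% of trials. For a mean 2 mmHg from the null, which is also the position if 4 mmHg is tested against the 2 mmHg sizing null, t-test power was 81-85% at skewness 0, ±0.5 and ±1.0. Two-stage power depended on the direction of skew: 66% or 92% at ±0.5, and 41% or 97% at ±1.0.

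**The case against.** The strongest reply has four parts.

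- **The null hypothesis does not name the mean.** If treatment changes nothing and a patient's two readings are exchangeable, the differences are symmetric about zero and Wilcoxon keeps its 5% level. This stands. The inflated rates are errors about the mean, not about H0 read as symmetry. It does not remove the mismatch, because the endpoint, estimand and sample size all name the mean.
- **Nothing in the documents points to skewed changes.** This stands. The one visible source of asymmetry, entry at Visit 2 only if BP is uncontrolled, was modelled with normal DBP readings cut at 80 mmHg (SD 9, correlation 0.3-0.7, all assumed). It gave skewness of only −0.01 to −0.08. At 0.3 the inflation is about one percentage point; it becomes material from about 0.5.
- **At the planned effect the verdict hardly changes.** This stands, as step 4 shows. The gap between mean and pseudo-median should not be set against the 2 mmHg distance used for sizing as though that were the planned test: the 2 mmHg null appears only in the sample-size text.
- **The rule is written down in advance and the mean stays visible.** Also true. A reader could rebuild the t-test and its interval from n, mean and SD. That limits the harm, but the planned primary p-value would still be the Wilcoxon one.

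A reader might infer that the primary analysis runs at 15-22% type I error, or that the trial's conclusion is unsafe. The documents support neither: those rates need a mean change of exactly zero together with skewness of 0.75 to 1.0, and the plan assumes 4 mmHg.

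**Conclusion.** The mismatch is real and follows from the text alone: the plan targets a mean, may test something else, and has no estimate or interval to go with that test. It should be corrected. The t-test stays within about half a percentage point of 5% in every row of the table, so the switch buys no validity at this sample size.

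The effect on error rates is conditional. It is nil for symmetric changes and reaches the tabulated rates only if changes are skewed and the mean change is truly zero. The likely effect on the trial's conclusion is small if the true change is near 4 mmHg and the test is against zero. It becomes appreciable for true changes of about 1-2 mmHg, or if the test is made against the 2 mmHg null. All of this assumes a 5% Shapiro-Wilk level and gamma-shaped skewness.

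**What to change.** In Protocol 14.5.2 and SAP 16.1.3, make the paired t-test with a 95% CI for the mean change the primary analysis whatever the Shapiro-Wilk result. Keep the Wilcoxon signed-rank test as a sensitivity analysis only. Make the same edit for SBP (Protocol 14.5.4, SAP 16.2.2) and for the exploratory Visit 1 to Visit 3 changes (Protocol 14.5.5, SAP 16.3.2).

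The cost is a few sentences and no new data. It is not purely editorial, however: Protocol 14.7 makes a change to the original primary analysis during the study the subject of a substantial amendment.

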#### 14.5.3 Sensitivity Analysis

The primary analysis will be conducted using the PP population.

#### 14.5.4 Secondary (efficacy) Analysis

Secondary efficacy variables will be summarized in a descriptive manner using both ITT and PP population.

- Change in mean sitting SBP between Week 0 (Visit 2) and Week 8 (Visit 3):
  - Change from baseline in sitting SBP from prior and post combination therapy will be compared using paired t-test. The p-value will be presented using a paired t-test comparing mean at baseline and mean at Week 8.
  - The secondary endpoint will be presented in a descriptive manner using n, mean, median, SD, Q1, Q3, and minimum and maximum.

Assumption of normality will be investigated using Wilk-Shapiro test. If violation is observed, then paired t-test will be replaced by Wilcoxon signed rank test.

The number of patients achieving BP goal (sitting BP ≤130/80 mmHg) will be summarized for Visit 2 and Visit 3, along with percentage. A p-value using McNemar's test will be presented to compare the proportion of patients achieving the BP goal (sitting BP ≤130/80 mmHg) between Visit 2 and Visit 3.

## 14.5.5 Exploratory (Efficacy) Analysis

Exploratory efficacy variables will be summarized in a descriptive manner using safety population for Visits 1, 2 and 3.

Identification Number: FORM-000050125

Previous Doc Number: CTWI10A

Version Number: 1.0, CURRENT

#### **Protocol Template**

Sponsor: Menarini Pharmaceutical Study Code: MEIN/19/ZoNe-HYP/001

Protocol Version\_1 of 16/07/2020

- Change in mean sitting SBP and sitting DBP between Visit 1 and Visit 3 will be analyze as following
  - Change from baseline in sitting SBP and DBP from prior (Visit 1) and post (Visit 3) combination therapy will be compared using paired t-test. The p-value will be presented using a paired t-test comparing mean at baseline and mean at Week 8.
  - The exploratory endpoint will be presented in a descriptive manner using n, mean, median, SD, Q1, Q3, and minimum and maximum.

Assumption of normality will be investigated using Wilk-Shapiro test. If violation is observed, then paired t-test will be replaced by Wilcoxon signed rank test.

The number of patients achieving BP goal (sitting BP ≤130/80 mmHg) will be summarized for Visit 1 and Visit 3, along with percentage. A p-value using McNemar's test will be presented to compare the proportion of patients achieving the BP goal (sitting BP ≤130/80 mmHg) between Visit 1 and Visit 3.

### 14.5.6 Subgroup Analysis

Subgroup analysis will be conducted using ITT and PP population based on the following parameters.

- Country/Site
- Age (<40 years and ≥40 years)

- Gender (Male, Female, Other)
- Presence of diabetes (patients with or without diabetes)
- Presence of hypercholesterolemia (patients with or without hypercholesterolemia)
- Screening therapy (ACE-i, Beta blocker)
- Run-in period therapy (Monotherapies of ZOF 30 mg or NEB 5 mg)

Identification Number: FORM-000050125

Previous Doc Number: CTWI10A

Version Number: 1.0, CURRENT

**Protocol Template** 

Sponsor: Menarini Pharmaceutical Study Code: MEIN/19/ZoNe-HYP/001

Protocol Version\_1 of 16/07/2020

#### 14.5.7 Safety Analysis

#### **Adverse Events:**

Adverse events recorded during the study will be mapped to a system organ class (SOC) and preferred term (PT) using the current Medical Dictionary for Regulatory Activities (MedDRA). Treatment-emergent adverse events are defined as new AEs that occur on or after the date/time of the first administration of study medication or worsen if an AE started prior to the start of first administration of study medication.

All the AEs will be presented with the following:

- Number of cases
- Number of patients with AE
- Percentage of patients with AE

#### Laboratory:

Laboratory parameters will be summarized descriptively using the safety population by visit. All laboratory data will be listed.

## ECG:

Electrocardiogram parameters will be summarized descriptively using the safety population by visit. All ECG data will be listed.

## **Physical Examination (PE):**

Physical examination parameters will be summarized descriptively using the safety population by visit. All PE data will be listed.

**14.5.8 Interim Analysis and Stopping Rules** Not applicable.

Identification Number: FORM-000050125

Previous Doc Number: CTWI10A

Version Number: 1.0, CURRENT

**Protocol Template** 

Sponsor: Menarini Pharmaceutical Study Code: MEIN/19/ZoNe-HYP/001

Protocol Version\_1 of 16/07/2020

#### 14.5.9 Data Imputations

As a part of missing data analysis Multiple Imputation (MI) simulation method for imputing missing data will be conducted on the primary efficacy endpoint using ITT population. This will help to assess the impact of missing data on the primary analysis.

The SAS procedure MI will be used, and the details of MI procedure will be stated in the dataset specification document. If the data is monotone missing, an imputation model with regression baseline parameters (age, gender, country/site, monotherapy and baseline values) will be applied, otherwise Markov Chain Monte Carlo (MCMC) will be applied. All variables included in the analysis model and values at Week 0 for the primary endpoint will be included in the imputation model. To reduce the sampling variability from the imputation process, 50 datasets will be generated.

In the estimation step, separate analysis will be performed using the paired t-test.

After the completion of the estimation step SAS procedure MIANALYZE will be used to pool the estimates.

#### 14.6 Protocol Deviations and Protocol Amendments

No deviations from the protocol should be initiated without prior approval by the EC/HA of a protocol amendment according to applicable regulations, except in case of emergency or when the change involves only logistical or administrative aspects of the trial.

Any deviation from the protocol, SOPs, GCP, and applicable regulatory requirements should be immediately reported to the Sponsor.

Changes in the study protocol will require a protocol amendment. Such amendments will be agreed upon and approved in writing by all signatories of the protocol.

If amendments are substantial, ie, are likely to have an impact on the safety of the patients, or to change the interpretation of the scientific documents in support of the conduct of the study, or if they are otherwise significant, the ECs and the country authorities (CAs) in the participating countries have to approve these amendments before implementation, according to applicable regulatory requirements.

Identification Number: FORM-000050125

Previous Doc Number:
CTWI10A

Version Number: 1.0, CURRENT

**Protocol Template** 

Sponsor: Menarini Pharmaceutical Study Code: MEIN/19/ZoNe-HYP/001

Protocol Version\_1 of 16/07/2020

Changes which have no significant impact on the medical or scientific validity of the study will be agreed upon and approved in writing by all signatories of the protocol and the EC, CAs (where applicable) will be notified of this protocol amendment.

Any substantial amendments of the protocol will be integrated in an updated study protocol. The PI must ensure full compliance with the updated study protocol.

## 14.7 Statistical Analysis Plan

This study is an open-label study and statistical analysis plan (SAP) will be finalized prior to first patient in. However, in case of any protocol amendment or any modification which may not affect the integrity of data or primary analysis but may lead to modification of SAP version, will be finalized prior to database lock. The SAP will describe in detail study endpoints and statistical analyses, including the analysis of the primary as well as additional endpoints. In case changes to the original primary endpoint or of the original primary analyses occurs during the study, these changes will be the subject of a substantial protocol amendment.

All statistical analyses not prespecified and run after database lock will be considered additional/exploratory analyses.

